7.10.1 Extent of exposure

See Section 7.8 above. Furthermore, as a measure of investigational product *in vivo* duration, patients' vaginal pH will be assessed on Day(s) 0 and 7. Vaginal pH lower at follow-up visits compared to Day 0 indicate appropriate release duration. Summary statistics on the vaginal pH will be presented.

7.10.2 Adverse Events

Adverse events will be coded according to MedDRA.

Only treatment-emergent adverse events, i.e. adverse events starting after administration of first dose of study treatment, will be presented as described below. Any adverse events reported to start before administration of first dose of study treatment will be listed separately. In the remainder of this section, the term "adverse event" should be interpreted as "treatment-emergent adverse event".

An overview of all adverse events will be presented, including the number and percentage of patients with at least one, and the total number, of the following:

- Adverse events.
- Serious adverse events.
- Adverse events leading to withdrawal of the investigational product.
- Fatal adverse events.
- Adverse events, broken down by severity (intensity).
- Adverse events, broken down by causality assessment (relationship).

The International Organization for Standardization (ISO) terms ADE, SADE, ASADE, USADE introduced in the CIP constitute adverse events where relationship to investigational device or study procedure is indicated. The classification of an untoward medical event as USADE or ASADE will be done retrospectively. The event will initially be captured as a serious adverse event.

The incidence of adverse events will be presented by system organ class and preferred term. For each system organ class and preferred term, the total number of adverse events as well as the number and percentage of patients with at least one adverse event in that system organ class or preferred term will be presented. The incidence of serious adverse events will be presented in the same way.

Separate tables for the incidence of adverse events broken down by severity and the incidence of adverse events broken down by causality assessment will also be presented by system organ class and preferred term.

There will also be tables on the most frequently reported adverse events, on system organ class level and on preferred term level. The decision on the frequency cut-off for these tables will be taken during the analysis of the adverse events data in consultation with the author of the clinical study report and could be influenced by factors such as the overall number of adverse events, study design, and the nature of the indication. The frequency cut-off should be mentioned in a table note.

Device deficiencies, as captured by the Device Event CRF module, will be presented in data listings only. If any device event is considered as also constituting an adverse event, it should be reported also as an adverse event.

7.10.3 Laboratory

The following laboratory variables are included in this study:

Microbiology assessments

- Assessment of BV according to Amsel's criteria performed? (Yes/No)
- Presence of at least 3 of the 4 Amsel's criteria stated in section 6.1 in CIP and SAP? (Present/Absent)
- Vaginal swab taken for culture? (Yes/No)
- Vaginal swab culture result (Positive/Negative)
 - If positive, species found should be indicated (5 categories + other)
- Vaginal swab taken for sequencing? (Yes/No) If No, specify reason (text)

Gynecological examination:

- Gynecological examination performed? (Yes/No)
- Vaginal pH (see Section 7.10.1 above)

The categorical microbiology laboratory parameters, as specified above, will be summarized in frequency tables by visit.

7.10.4 Physical examination

Not applicable.

7.10.5 Vital signs

Not applicable.

7.10.6 Electrocardiogram

Not applicable.

7.11 Changes to planned analysis

A clarification regarding the secondary endpoint

- Proportion of patients receiving prolonged treatment

is made. This endpoint is obviously intended to be based on "All patients". However, in the CIP, this endpoint was unintentionally listed under the heading "For patients receiving prolonged treatment". In this document it has therefore been listed in the correct heading "All patients".

A subgroup analysis, based on whether the patients at Day 0 reported 3 or more Bacterial Vaginosis infections during the last 12 months or not, has been added for the primary clinical performance endpoint, see [Section 7.1.8](#) above.

8 Derived variables

8.1 Disposition of patients

A screening failure is defined as a screened but not enrolled patient. An enrolled patient is defined as having passed the screening procedures and given informed consent. An enrolled patient who has received at least 1 dose of study treatment is qualified to be included in FAS.

8.2 Demographics and baseline characteristics

8.2.1 Age

Age will be computed as the integer part of the time in years between the date of birth and the date the written informed consent was signed, using the SAS function `yrdif()` with the basis parameter set to 'age'. For patients for whom only the year of birth is collected, age will be computed as the difference between the year the informed consent was signed and the year of birth.

8.3 Body mass index

Not applicable.

8.4 Change from baseline

Change from baseline will be computed as the difference between a post-baseline value and the corresponding baseline value. This is applicable for the change in the sum of the 3 BV symptom scores (fishy smell, burning, and irritation) from Day 0 to specified follow-up visits, as well as for vaginal pH from Day 0 to Day 7.

8.5 Clinical cure rate

Clinical cure rate is based on a binary variable, where a clinically cured patient is defined as absence of all of the following Amsel criteria:

- Thin, white, yellow, homogenous discharge
- Clue cells on microscopy (more than 20% of epithelial cells)
- Release of fishy odor "i.e. a positive whiff test" when alkali (10% potassium hydroxide [KOH] solution) is added

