4.2 Inclusion Criteria

- Adult, post-menarchal, pre-menopausal women aged 18 years or older
- Diagnosis of BV according to Amsel's criteria, defined as having 3 out of 4 of the following criteria:
 1. Thin, white, yellow, homogenous discharge
 2. Clue cells on microscopy (more than 20% of epithelial cells)
 3. pH of vaginal fluid above 4.5
 4. Release of fishy odor "i.e. a positive whiff test" when alkali (10% potassium hydroxide [KOH] solution) is added.
- Having decisional capacity and providing written informed consent.
- Negative urine pregnancy test at screening.
- Refrain from using any intravaginal products (i.e., contraceptive creams, gels, foams, sponges, lubricants, or tampons, etc.) during the study period.
- Refrain from sexual intercourse or use a condom until Day 7.
- Signed informed consent and willing and able to comply with all study requirements.

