5.7 Prior and Concomitant Medication

Information about any concomitant medication, including OTC medications and vitamins taken by patients during the study and within 14 days prior to inclusion shall be documented in the eCRF. The generic name or trade name, dosage, and reason for use shall be recorded for all medications.

NOTE: Antibiotic medication during the study and within 14 days prior to inclusion is strictly prohibited

See [Appendix 1, Section 3](#) for specific questions.

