The decision on the classification of patients to each analysis set will be taken at the clean file meeting and documented in the clean file report together with the reasons for excluding patients from analysis sets.

7.2.1 *Full analysis set*

Full Analysis Set (FAS): This is the primary population and comprises all patients entering the study and having received at least 1 dose of study treatment. Analyses of clinical performance will be performed against this population.

In addition to this, two sub-populations based on this FAS will be formed: “FAS (For patients not receiving prolonged treatment)”, and “FAS (For patients receiving prolonged treatment)”.

7.2.2 *Per-protocol analysis set*

Per Protocol (PP) Population - This will include all FAS patients without any major protocol deviation, i.e. patients who have completed the study and sufficiently complied with the study protocol, have available primary endpoint data and have received the study treatment according to protocol. The final definition of a major protocol deviation will be decided and defined at the clean file meeting and

documented in the clean file report. If a relevant number of patients are excluded from the PP population, then the analysis of the clinical performance endpoint will be provided for the PP population.

7.2.3 *Safety analysis set*

The safety analysis set will be based on the same definition as used for FAS. All safety analyses will therefore be performed against the FAS. All patients included in the FAS will be accounted for, including those who did not complete the study along with the reasons for withdrawal.

7.3 *Disposition of patients*

The following will be presented:

- Number of screened patients, in total.
- Number of screening failures, in total.
- Number of enrolled patients.

Based on the number of enrolled patients, the following will also be presented:

- Number and percentage of patients who did not receive any dose of study treatment.
- Number and percentage of patients who received at least one dose of study treatment.
- Number and percentage of patients who completed the study.
- Number and percentage of patients who withdrew prematurely from the study.
- Number and percentage of patients in each of the analysis sets.

In addition, a frequency table on the primary reason for premature withdrawal from the study will be presented. Percentages for this table will be based on the number of prematurely withdrawn patients.

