7.9 Primary and secondary endpoints analyses

All analyses of clinical performance endpoints will be performed on the full analysis set, and these analyses will be considered as the main analyses. If a relevant number of patients are excluded from the PP population, the per-protocol analysis set will be used for supportive clinical performance sensitivity analysis of the primary clinical performance endpoint.

If the stated assumptions that the statistical evaluation is built upon can be questioned, suitable alternative methods may be applied. For example, a 95% confidence interval based on a non-parametric method may be applied if assumption of data belonging to the normal distribution seems not to hold.

All study endpoints (primary, secondary, and exploratory), as well as the related variables specified in the list below in Section 7.9.2, will be presented descriptively.

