Below follows a list of all secondary endpoints followed by information on which are binary and which are continuous. Note that, as described in [Section 3.2.1](#) above, the analyses of the secondary endpoints will be performed on 3 different patient categories. These are denoted as A, B, and C below.

A. All patients

- i] Proportion of patients being negative for each of the 3 Amsel criterion on Day 7 compared to Day 0
- ii] Proportion of patients having a reduction in the sum of the 3 BV symptoms scores (fishy smell, burning, and irritation) on Day 4 and Day 7, compared to Day 0
- iii] Change in the sum of the 3 BV symptoms scores (fishy smell, burning, and irritation) from Day 0 to Day 4 and Day 7
- iv] Proportion of patients receiving prolonged treatment
- v] Usability, measured by patient questionnaire

The endpoints i], ii], iv], and the first 4 questions in endpoint v] are binary variables.

The endpoints iii], and the 5th question in v] are considered as continuous variables.

B. For patients not receiving prolonged treatment

- vi] Recurrence rate on Day 14 and Day 35, defined as the proportion of patients clinically cured on Day 7 and thereafter responding "yes" to a yes/no question from the patient questionnaire on whether the symptoms have recurred

The endpoint vi] constitute binary variables.

C. For patients receiving prolonged treatment

- vii] Clinical cure rate on Day 14, defined as the absence of all of the 3 Amsel criteria as defined above
- viii] Proportion of patients being negative for each of the 3 Amsel criterion on Day 14 compared to Day 0
- ix] Proportion of patients having a reduction in the sum of the 3 BV symptoms scores (fishy smell, burning, and irritation) on Day 11, Day 14, Day 21, and Day 42, compared to Day 0
- x] Change in the sum of the 3 BV symptoms scores (fishy smell, burning, and irritation) from Day 0 to Day 11, Day 14, Day 21, and Day 42
- xi] Recurrence rate on Day 21, and Day 42, defined as the proportion of patients clinically cured on Day 14 and thereafter responding “yes” to a yes/no question from the patient questionnaire on whether the symptoms have recurred
- xii] Proportion of patients receiving rescue treatment on Day 14

The endpoints vii], viii], ix], xi], and xii] are binary variables.

The endpoints x] are considered as continuous variables.

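### Day 7 cure has no scoring rule for a woman who took a prohibited antibiotic or other BV treatment, so an assisted cure would count for the pessary in the primary analysis

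*SAP*

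**What the plan says.** **Endpoint.** SAP 8.5 derives clinical cure from three Amsel signs (discharge, clue cells, whiff test): "a clinically cured patient is defined as absence of all of the following Amsel criteria". Protocol 2.1 and 6.1 and SAP 3.1.1 and 6.1 define it the same way. None of them mentions other treatment.

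**Population.** Under SAP 7.2.1 the FAS "comprises all patients entering the study and having received at least 1 dose of study treatment". SAP 7.9 adds: "All analyses of clinical performance endpoints will be performed on the full analysis set, and these analyses will be considered as the main analyses". SAP 7.1.5 uses observed data without imputation.

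**Other treatment.** Protocol 5.7 states: "Antibiotic medication during the study and within 14 days prior to inclusion is strictly prohibited". An inclusion criterion in protocol 4.2 reads "Refrain from using any intravaginal products" for the study period. Neither says how cure is scored if the rule is broken.

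**What happens to a woman who breaks it.**
- Protocol 4.4 and 4.5 allow the investigator to withdraw a non-compliant patient but do not require it.
- Concomitant medication is recorded at each contact. SAP 7.7 classifies and tabulates it.
- SAP 7.4 lists protocol deviations.
- SAP 8.10, the one endpoint built on medication data, counts only rescue treatment started on or after Day 14.
- The per-protocol set depends on a definition of major deviation that SAP 7.2.2 leaves to the clean file meeting. SAP 7.9 makes its analysis supportive and conditional: "If a relevant number of patients are excluded from the PP population".

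**Day 14.** The secondary endpoint for women on prolonged treatment uses the same three signs: "Clinical cure rate on Day 14, defined as the absence of all of the 3 Amsel criteria as defined above".

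**The concern.** The primary objective is the clinical performance of the pessary. As written, the endpoint measures absence of signs on Day 7 by whatever means. A woman who starts an antibiotic for another infection during the first week, or who treats herself for BV, stays in the FAS unless someone chooses to withdraw her. If her signs have gone, she adds one to the numerator.

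No concurrent arm exists in which such use could balance out. The comparison is with a fixed 40%, and a treatment that can clear BV can only raise the count. The per-protocol analysis might show the effect, but one or two women may not be judged enough to trigger it. That judgement comes late in an open-label trial in which Day 7 status has already decided who gets prolonged treatment. Without a rule, the handling of a patient who could decide the result is settled after her outcome is known.

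**Working it through.** **Inputs.** Null rate 40%, one-sided 95% Clopper-Pearson limit (SAP 7.9.1). True rate 70%, 22 evaluable patients, 24 included, stated power 90% (SAP 5.1). Antibiotic cure of BV usually 70% to 80% (protocol 1.1); 75% is used as the midpoint. The share of women using an antibiotic or other BV treatment before Day 7, *u*, is not in the documents. I assume 1%, 2% and 5%.

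**1. The plan's own figure.** Normal approximation: n = [(1.645·√(0.4·0.6) + 1.282·√(0.7·0.3)) / 0.3]² = 21.56, rounded up to 22. This reproduces. Under the exact rule that the SAP will apply, power at 70% is 81.4% with 22 (14 cures needed) and 84.7% with 24 (15 needed). The 84.7% is the baseline below.

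**2. The boundary.** Lower limit = 5th percentile of Beta(x, n − x + 1). With n = 24:

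| Cures | Lower limit | Result |
|---|---|---|
| 14 | 39.7% | fails |
| 15 | 43.7% | passes |

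Type I error is P(X ≥ 15 | 24, 0.40) = 0.022. One cure separates failure from success.

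**3. A given number of users, pessary rate 40%.** If all k users are scored cured, type I error is P(X ≥ 15 − k | 24 − k, 0.40): 0.035 for k = 1 and 0.055 for k = 2. If each user is cured with probability 70% to 80%, it is 0.028 to 0.031 and 0.037 to 0.042.

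**4. Averaged over how many women use such treatment.** Let use be independent of pessary response, and let a user be cured if either treatment works. The rate of scored cures is then p + u·(1 − p)·0.75.

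| u | Scored rate at p = 40% | Type I error | Success at p = 60% | Success at p = 70% |
|---|---|---|---|---|
| 0 | 40.00% | 0.022 | 48.9% | 84.7% |
| 1% | 40.45% | 0.024 | 50.1% | 85.3% |
| 2% | 40.90% | 0.027 | 51.3% | 85.9% |
| 5% | 42.25% | 0.037 | 55.0% | 87.5% |

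The gain is about 1, 2 and 6 points at a true 60%, and 0.6, 1.2 and 2.8 points at 70%.

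**5. When the nominal 5% would be passed.** The scored rate must exceed 43.7%, the lower limit at 15 of 24. Under step 4 this needs u = 0.0371 / (0.6 × 0.75) = 8.2%. If every user came from the women the pessary had not cured, it needs u = 0.0371 / 0.75 = 4.9%.

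**6. Cost of scoring users as not cured.** Power at 70% is P(X ≥ 15 | 24 − k, 0.70): 77.1% for k = 1 and 67.1% for k = 2. Type I error falls to 0.013 and 0.007.

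**The case against.** The best defence is that analysing observed outcomes in all treated women is a stated choice, and that the plan is not blind to the problem. Antibiotic use at entry or in the previous 14 days is an exclusion, so only new starts within about a week matter. The investigator may withdraw a non-compliant patient. Deviations and medications are reported, so with 24 women a reader could see an antibiotic user behind a result of 15 of 24. Protocol 9.1 allows sensitivity analyses. All of this stands, but it gives visibility and leaves the primary result unchanged.

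Three stronger readings are tempting, and the documents do not support them.

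- **A large effect.** Under the assumed 1%, 2% and 5%, the chance of at least one user among 24 is 1 − (1 − u)²⁴ = 21%, 38% and 71%. A reader might take these as chances of a changed result. A change also needs the user to be someone the pessary did not cure, the other treatment to clear her signs, and the count to sit at the boundary.
- **A near-certain cure for any user.** Protocol Table 1 reports regimens given for BV, with ranges from 26–46% to 70–100%. It says nothing about an antibiotic chosen for a throat or urinary infection and taken for a few days, which may cure BV less often.
- **Day 14 as part of the primary test.** It is a secondary endpoint in women on prolonged treatment, with a two-sided interval and no 40% threshold.

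The proposed rule also has a cost: it biases against the product.

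**Conclusion.** The gap is real. Followed as written, the plan credits the pessary with any Day 7 cure reached with the help of a prohibited antibiotic or other BV treatment, and no existing safeguard alters the primary result. One such cure could decide the trial at the 14/15 boundary.

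The expected size is small. Type I error stays below the nominal 5% at assumed use of 1% to 5% if use is unrelated to pessary response. It reaches about 5% at 4.9% use only if every user is a woman whom the pessary had not cured. Two users both certain to be scored cured would give 0.055. All of these figures rest on assumed use, and actual use may be zero. The case for a rule is that it is cheap and removes a decision that would otherwise be made with the outcome in view. It is worth making, but the documents do not show that the trial's conclusion is likely to be wrong.

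**What to change.** Add to SAP 8.5: *A patient with a recorded systemic or vaginal antibiotic, or any other treatment for BV, started after the first dose and before the Day 7 assessment is counted as not cured on Day 7 in the primary analysis, whatever the Amsel findings. The as-observed result is given as a sensitivity analysis.* Apply the same scoring rule to the secondary Day 14 cure rate, for treatment started after the first dose and before the Day 14 assessment. Rescue treatment prescribed as a result of that assessment does not count. Record the addition in SAP 7.11.

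No new data are needed, because concomitant medication is already collected at each contact. The price is that a woman the pessary would have cured anyway is scored as a failure, with the loss of power shown in step 6. If nobody uses such treatment, nothing changes.

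This is a scoring rule for the analysis only. Separately, protocol 5.7 prohibits antibiotics throughout the study while protocol 5.2.1 foresees them as rescue on Day 14 and at withdrawal. The sponsor should reconcile the two sections.

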8.6 Proportion of patients being negative for each of the Amsel criteria

The proportion of patients being negative for each of the Amsel criteria is based on binary variables.

A patient being negative for Amsel criterion 1 is defined as a patient with absence of the following Amsel criterion:

- Thin, white, yellow, homogenous discharge

A patient being negative for Amsel criterion 2 is defined as a patient with absence of the following Amsel criterion:

- Clue cells on microscopy (more than 20% of epithelial cells)

A patient being negative for Amsel criterion 3 is defined as a patient with absence of the following Amsel criterion:

- Release of fishy odor "i.e. a positive whiff test" when alkali (10% potassium hydroxide [KOH] solution) is added

The endpoints related to this, see [Section 3.2.1](#) above, are phrased "Proportion of patients being negative for each of the 3 Amsel criterion on Day 7 compared to Day 0", and "Proportion of patients being negative for each of the 3 Amsel criterion on Day 14 compared to Day 0". These endpoints will be calculated as stated in [Section 8.6](#), i.e. without consideration of Day 0 values, but the number of patients being negative at Day 0 will be stated in a footnote in the result tables for these endpoints.

8.7 Proportion of patients having a reduction in the sum of the 3 BV symptoms scores

The proportion of patients having a reduction in the sum of the 3 BV symptoms scores (fishy smell, burning, and irritation) compared to Day 0 is based on a change from baseline variable, see [Section 8.4](#) above, where a patient with reduction is defined as when the change from baseline in the sum of the 3 BV symptoms scores is < 0. If at least one symptom score is missing, the sum of the 3 BV symptoms scores will be set to missing.

8.8 Recurrence rate

Recurrence rate is based on a binary variable, where a recurred patient is defined as a patient clinically cured on Day 7 and thereafter responding "yes" at specified follow-up visits to a yes/no question from the patient questionnaire on whether the symptoms have recurred.

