3.2.1 Secondary endpoints

Secondary endpoints:

All patients

- Proportion of patients being negative for each of the 3 Amsel criterion on Day 7 compared to Day 0
- Proportion of patients having a reduction in the sum of the 3 BV symptoms scores (fishy smell, burning, and irritation) on Day 4 and Day 7, compared to Day 0

- Change in the sum of the 3 BV symptoms scores (fishy smell, burning, and irritation) from Day 0 to Day 4 and Day 7
- Proportion of patients receiving prolonged treatment
- Usability, measured by patient questionnaire

For patients not receiving prolonged treatment

- Recurrence rate on Day 14 and Day 35, defined as the proportion of patients clinically cured on Day 7 and thereafter responding “yes” to a yes/no question from the patient questionnaire on whether the symptoms have recurred

For patients receiving prolonged treatment

- Clinical cure rate on Day 14, defined as the absence of all of the 3 Amsel criteria as defined above
- Proportion of patients being negative for each of the 3 Amsel criterion on Day 14 compared to Day 0
- Proportion of patients having a reduction in the sum of the 3 BV symptoms scores (fishy smell, burning, and irritation) on Day 11, Day 14, Day 21, and Day 42, compared to Day 0
- Change in the sum of the 3 BV symptoms scores (fishy smell, burning, and irritation) from Day 0 to Day 11, Day 14, Day 21, and Day 42
- Recurrence rate on Day 21 and Day 42, defined as the proportion of patients clinically cured on Day 14 and thereafter responding “yes” to a yes/no question from the patient questionnaire on whether the symptoms have recurred
- Proportion of patients receiving rescue treatment on Day 14

Exploratory endpoint variables:

All patients

- Effect on vaginal microbiome on Day 0 and Day 7
- Vaginal pH on Day 7

For patients not receiving prolonged treatment

- Effect on vaginal microbiome on Day 35

For patients receiving prolonged treatment

[figure not shown]
- Effect on vaginal microbiome on Day 14 and Day 42

4 Study design

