This is an open-label, single-armed, multi-center study to evaluate clinical performance, tolerability, and safety of Gedeo Pessary in 24 adult women with BV. Patients seeking treatment can be screened for study participation. Included patients will have gynecological examination, including collection of vaginal samples, and will receive the investigational product to be self-administered at Day(s) 0, 2, 4, and 6. Patients will again be examined after 7 days. Prolonged treatment at Day(s) 7, 9, 11, and 13 will

be given to patients not cured at Day 7; including re-examination at Day 14. Patients will be followed up by telephone up to 29 days after last treatment administration. Gynecological examinations include collection of Amsel criteria. Vaginal samples will be used for confirming diagnosis and microbiome analyzes. Patient questionnaires will be used for assessing BV symptoms, usability, and AEs.

Figure 1 Study Flow Chart

AC = Amsel's Criteria, BVS = Bacterial Vaginosis Symptoms, VS = Vaginal Swab (*Self-swab at home)

Patients not receiving prolonged treatment applies to patients cured at Day 7. If not cured, the flow chart *patients receiving prolonged treatment* applies. Patients will here receive an antibiotic if not cured at Day 14. Adverse events will be assessed throughout the study.

5 Study population

This study will include patients with BV. Twenty-four (24) patients are planned to be treated under this CIP

Post-menarchal, pre-menopausal females aged 18 years or older seeking treatment for symptoms of BV at study sites' gynecological clinics may be informed about the study and asked about their willingness to participate.

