7.1.1 Presentation of results

If applicable, results will be presented together with the unit.

Continuous data will be summarised using descriptive statistics, and the following parameters will be reported:

- number of patients with evaluable observations and missing observations
- arithmetic mean and standard deviation
- median
- first and third quartiles
- minimum and maximum.

Categorical data will be presented using absolute frequency and percentage. When the absolute frequency is zero, the percentage will not be presented. Unless stated otherwise, the denominator for percentage calculations will be the total number of patients in the applicable analysis set, including patients with missing data. For variables with missing values, the number and percentage of patients with missing values will be presented.

Statistical testing will be performed using an overall significance level of 5%. The primary endpoint analysis will be based on one-sided testing, whereas the secondary endpoints analyses will be based on two-sided testing. Corresponding confidence intervals will be presented. See Section 7.9 below for further information.

Data will be presented using an appropriate number of decimal places, to ensure that undue precision is not implied (e.g. the number of decimals should not exceed the accuracy of the measuring instrument). Raw data will be presented with the same number of decimals as collected, and derived data with an appropriate number of decimals based on general practice, mathematical rationale or scientific rationale.

Minimum and maximum values will be presented with the same number of decimals as the analysed variable and the other descriptive statistics will be presented with one decimal more. Percentages and proportions will be presented with one decimal. Confidence interval bounds will be presented with the same number of decimals as the corresponding point estimate, and p-values will be presented with 4 decimals or as '<.0001'.

Mock tables and graphs are presented in the Data Display Plan (DDP), which is a supplementary document to this analysis plan. Individual patient data listings will be presented according to the ICH E3 guideline for Structure and Content of Clinical Study Reports (2), unless stated otherwise.

7.1.2 *Baseline*

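### SAP 8.8 ties recurrence to cure on Day 7 for every patient, but the Day 21/42 recurrence endpoint in prolonged-treatment patients requires cure on Day 14

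*SAP*

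**What the plan says.** The derivation is in SAP 8.8: "a recurred patient is defined as a patient clinically cured on Day 7 and thereafter responding" yes at the specified follow-up visits. The same rule serves all recurrence endpoints.

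The endpoint for patients receiving prolonged treatment is worded differently. SAP 3.2.1 has "Recurrence rate on Day 21 and Day 42, defined as the proportion of patients clinically cured on Day 14 and thereafter responding" yes, and endpoint xi in SAP 7.9.2 repeats it: "Recurrence rate on Day 21, and Day 42, defined as the proportion of patients clinically cured on Day 14 and thereafter responding" yes. SAP 6.1 and the protocol synopsis, 2.2 and 6.1 agree.

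On who belongs to that group, SAP section 4 says that prolonged treatment will "be given to patients not cured at Day 7; including re-examination at Day 14".

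Two other sections could in principle have settled the matter. SAP 8.5 defines cure ("a clinically cured patient is defined as absence of all of the following Amsel criteria") but names no day. SAP 7.11 lists the changes to the planned analysis. It contains "A clarification regarding the secondary endpoint" on the proportion receiving prolonged treatment, and an added subgroup analysis, but nothing on recurrence.

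**The concern.** Section 8 of the SAP is where a programmer looks for the rule that turns collected data into analysis variables. For the prolonged-treatment group, the rule found there selects on a condition that the group fails by design. Derivation and endpoint definition therefore give different answers from the same data, and the answer from 8.8 flatters the product: no recurrence among women whose first course had failed. Recurrence is a named secondary endpoint reported with an exact two-sided 95% interval, so a structural zero would appear in the results as if it had been observed.

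**Working it through.** The plan gives no figure for this endpoint, so there is none to reproduce. The check is a comparison of text followed by an illustration of scale.

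**Step 1: the conditions side by side**

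| Source | Group | Cure required on | Recurrence asked on |
|---|---|---|---|
| SAP 7.9.2, endpoint vi | Not prolonged | Day 7 | Day 14, Day 35 |
| SAP 7.9.2, endpoint xi; SAP 3.2.1, 6.1; protocol synopsis, 2.2, 6.1 | Prolonged | Day 14 | Day 21, Day 42 |
| SAP 8.8 | No distinction | Day 7 | Specified follow-up visits |

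SAP 8.8 matches endpoint vi only.

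**Step 2: overlap with the prolonged group.** Entry to prolonged treatment means not cured on Day 7 (SAP section 4, protocol 3.1). Being recurred under 8.8 means cured on Day 7. By design no patient satisfies both, so the count is zero regardless of the answers on Day 21 and Day 42.

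There is one edge case. SAP 8.9 classes a patient as prolonged if any dose was taken on Day 7, 9, 11 or 13. A patient cured on Day 7 who took a late dose that day could therefore be placed in the group. Hence essentially zero rather than exactly zero.

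**Step 3: expected size of the group.** Inputs: 24 patients and a 70% true cure rate (SAP 5.1). It is assumed that all 24 are assessed on Day 7 and that everyone not cured enters prolonged treatment.

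- Expected prolonged patients: 24 × (1 − 0.70) = 7.2, so about 7.
- Central 95% range of Binomial(24, 0.30): 3 to 12.

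**Step 4: what 8.8 would report.** With zero events the two-sided 95% Clopper-Pearson upper limit is 1 − 0.025^(1/n).

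- n = 7: 1 − 0.025^(1/7) = 0.410, giving 0/7 (0 to 41.0%).
- n = 3: 0/3 (0 to 70.8%).
- n = 12: 0/12 (0 to 26.5%).

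**Step 5: what the endpoint definition could report.** The documents give no Day 14 cure rate. If 30% to 70% of the 7.2 patients were cured on Day 14 (an assumption), then 7.2 × 0.30 = 2.2 to 7.2 × 0.70 = 5.0, or about 2 to 5 patients, could go on to count as recurred. SAP 8.8 counts none of them.

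As one worked case, again with assumed counts and answers taken at Day 42: 7 prolonged patients, 4 cured on Day 14, 2 of these answering yes.

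| Rule | Recurred | Over all 7 | Over the 4 cured on Day 14 |
|---|---|---|---|
| SAP 8.8 as written | 0 | 0/7 = 0% (0 to 41.0%) | not applicable |
| Endpoint xi | 2 | 2/7 = 28.6% (3.7 to 71.0%) | 2/4 = 50.0% (6.8 to 93.2%) |

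The discrepancy is in the numerator and is present on either denominator.

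**The case against.** The strongest reply is that the intended rule is not in doubt. Six places state the Day 14 condition. One of them, endpoint xi in SAP 7.9.2, sits in the analysis section and fixes group, cure visit and question visits. SAP 8.8 itself refers to specified follow-up visits and so leans on those lists. Applying it to the prolonged group is plainly impossible, and a careful programmer would notice. All of this is fair: it makes the error a slip and limits its weight. It does not make 8.8 correct. The section states an explicit and different rule, and neither 8.5 nor 7.11 repairs it.

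It is also fair that the worked case rests on assumed counts. Only the 24 patients and the 70% come from the documents. The contradiction needs none of these numbers.

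A reader might go further and infer that the recurrence denominator is wrong as well. The documents do not support that. By default, SAP 7.1.1 says that "the denominator for percentage calculations will be the total number of patients in the applicable analysis set, including patients with missing data", and SAP 7.2.1 forms the two sub-populations to which this applies. The endpoint wording can mean a rate among cured patients, or the proportion of the sub-population who are both cured and answer yes. The Data Display Plan, which holds the mock tables and was not available, may settle it. This is a separate ambiguity. Insisting on a rate among the cured would assume the disputed reading, and would still leave open how to treat cured patients who are not reached at follow-up.

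**Conclusion.** SAP 8.8 is wrong as written for patients receiving prolonged treatment. It forces the Day 21 and Day 42 recurrence count to essentially zero, for example 0/7 (0 to 41.0%) at the planned cure rate. This conclusion rests only on the text of 8.8, the endpoint definition and the rule for entering prolonged treatment. The group size of about 7 additionally assumes the planned 70% cure rate and complete Day 7 assessment.

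The reach is limited: one descriptive secondary endpoint in a small subgroup. A reader might infer that the trial's main result or all recurrence results are compromised, but the documents do not bear this out. The primary endpoint is cure on Day 7 and does not use 8.8. SAP 7.9.2 excludes hypothesis tests on binary secondary endpoints. The Day 14/35 recurrence endpoint already agrees with 8.8. Nor do the documents show that a zero will in fact be reported; they show only that the written derivation would produce one.

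**What to change.** Rewrite SAP 8.8 with one rule per group:

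- Patients not receiving prolonged treatment: recurred on Day 14 or Day 35 if clinically cured on Day 7 and answering yes to the recurrence question at that visit.
- Patients receiving prolonged treatment: recurred on Day 21 or Day 42 if clinically cured on Day 14 and answering yes at that visit.

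This restores the protocol's own definition. It costs a change of SAP wording, with no new data, no protocol amendment and no effect on sample size or the primary analysis. It should be made before the recurrence variables are programmed.

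Separately, the sponsor may wish to say whether the denominator is the whole sub-population, as under the 7.1.1 default, or the patients cured at the reference visit. The correction to 8.8 does not depend on that choice.
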